### 3. Introduction

Suicide Remains a Significant Public Health Problem. With 44,965 U.S. suicides in 2016 (one suicide every 11.7 minutes), suicide remains the 10th leading cause of death among all ages and the second leading cause of death among those 10-44 years old. Despite considerable effort, U.S. suicide rates have remained unchanged for over two decades. In 2012, 483,596 people were treated in Emergency Departments (EDs) for suicide attempts and non-suicidal self-injury; 332,833 were hospitalized. The U.S. cost of suicides and suicide attempts in 2013 was \$58.4 billion – of this 97% was due to lost productivity; adjusted for underreporting, \$94.5 billion or \$298 per capita. While it might be hoped that hospitalization may resolve suicide risk, it significantly increases (up to as much as 200 times) for individuals recently discharged.

EDs face formidable challenges in treating these patients that ultimately result in significantly longer lengths of stay compared to those for medical emergencies, lower satisfaction, and unnecessary hospitalizations. Jaspr is an evidence-based patient, and provider facing tablet application that has been funded through a National Institute of Mental Health (NIMH) SBIR grant (R44MH108222) and built by suicide experts and people with lived suicide experience. Jaspr is designed to reduce unnecessary hospitalization, length of stay (LOS) in the emergency department (ED), and ED/hospital readmissions while also improving patient satisfaction. Jaspr enables delivery of four of the five brief interventions recommended by the Suicide Prevention Resource Center (SPRC) including brief patient education, safety planning, lethal means counseling, and caring contacts post-discharge.

*For the patient, Jaspr has four primary sections:*

1. Suicide Risk Assessment: Through the use of a virtual guide, Jaspr walks the patient through the Collaborative Assessment and Management of Suicidality (CAMS) - an evidence-based suicide risk assessment that includes crisis and lethal means safety planning. Data from the assessment will be provided to the provider as a decision support tool in report form and the crisis safety and lethal means safety plans will be available for the patient to take home. CAMS was developed by [name] for use by clinicians to engage, assess, and treat suicidal patients.

CAMS was developed by [name] for use by clinicians to engage, assess, and treat suicidal patients. CAMS is a non-prescriptive, atheoretical therapeutic framework for patients drawn to suicide as a way of coping. CAMS is a highly flexible treatment that can be used as a brief intervention, as an add-on to an existing treatment, or as a short-term (6-8 session) treatment. CAMS is a highly collaborative method for understanding and treating patient-defined “drivers” for suicide. CAMS is guided by the “Suicide Status Form” (SSF) which is used to assess the patient’s own ratings of suicide risk, including reasons for living and dying (Section A), along with key suicide risk and warning signs relevant to imminent risk (Section B), which lead to stabilization planning, suicide-specific treatment, and a better-informed disposition for care (Section C). CAMS Stabilization Plan includes: reducing access to lethal means, developing specific behavioral strategies to enhance coping with future suicide crises, and identifying people to call for help, which is supplemented by specific treatment goals and driver-specific interventions. Three published RCTs (Comtois et al., 2011; Andreasson et al., 2016; Jobes et al., 2017), eight non-randomized trials (Jobes, Jacoby, Cimbolic, & Hustead, 1997; Ellis, Rufino, Allen, Fowler, & Jobes, 2015; Ellis, Green, Allen, Jobes, & Nadorff, 2012; Arkov, Rosenbaum, Christiansen, Jonsson, Munchow, 2008; Jobes, Kahn-Green, Greene, & Goeke-Morey, 2009; Nielsen, Alberdi, & Rosenbaum, 2011; Jobes, Wong, Conrad, Drozd, & Neal-Walden, 2005; Ellis, Rufino, & Allen, 2017), and two not yet published RCTs across multiple treatment settings provide replicated evidence that CAMS reliably outperforms control conditions in reducing suicidal ideation, overall symptom distress, and depression, while increasing hope, patient satisfaction, and care retention. Recent RCTs provide promising evidence that CAMS reduces self-harm and suicide attempts (Andreasson et al., 2016) and that standard CAMS significantly decreases ED visits among

suicidal military sub-samples (Jobes et al., 2005; Huh et al., 2017).

2. Shared Stories: The app contains a robust collection of videos from people who have lived experience with suicide sharing their personal stories to inspire hope and connectedness that the patient can browse either by topic category or by the individual story teller.
3. Comfort and Skills: Through a variety of activities and videos, the app teaches the patient coping skills to manage their imminent distress in the moment and reduce their suicide risk post-discharge.
4. Take Away Kit (“Jaspr-at-Home”): A companion mobile app accompanies the patient home for continued use during the highest period of suicide risk post-discharge. The patient has the ability to save activities and videos from the app to their crisis safety plan which is then available to them post discharge. Additionally, there are more advanced skill building tools and activities available to the patient post discharge that can be customized by the provider.

*For the provider:*

- Jaspr will generate a provider decision support report based on the CAMS interview that can be printed or faxed to the provider. In the future (but not during the length of this study), the patient data will be integrated into the EMR.
- Allow the provider to select additional skills and activities that will be available to the patient post discharge.
- Create custom “Caring Contacts” that will be delivered to the patient at definable intervals post discharge

This NIMH-funded research involves two research phases: a **formative evaluation** and a **summative evaluation**.

The formative evaluation (SIRB #7097) occurred first and will continue throughout the length of the research project. Its purpose is to gather invaluable information as we design and improve all features for patient and provider users of the technology to ensure its acceptability, ease of use, and clinical relevance to achieve the intended outcomes, such as: decreasing suicidal behavior, length of stay in the ED, unnecessary hospitalization, readmission, liability, and increasing ability to manage suicidal crises and satisfaction with ED experience.

The focus of this summative evaluation is to evaluate Jaspr (N=120) and JAH (N=60) in clinical trials. The ED clinical trial compares Jaspr to Care-as-Usual (CAU) in EDs nationwide; the Telehealth clinical trial compares JAH to CAU + crisis safety plan. Patient participants meeting study criteria for the ED study will be randomly assigned to receive Jaspr (in addition to their usual care; n=60) or CAU only (the treatment that is standardly provided to suicidal patients in the ED; n=60). Patients participants in the ED study who are assigned to the Jaspr condition will receive access to JAH for use throughout the follow up period as they see fit. Outpatient participants meeting study criteria for the Telehealth study will be randomly assigned to receive JAH (in addition to their usual care; n=30) or CAU (in addition to crisis safety planning; n=30). We will also conduct a small (N=15) ED study pilot trial to make necessary adjustments to both study procedures and Jaspr before conducting the ED study RCT. The research procedures for the pilot and full RCT will be identical unless the research team identifies areas for improvement during the pilot to incorporate into the full RCT. All modifications will be submitted to IRB prior to implementation.

Patient participants in the ED study will be asked to complete study sessions (interview and online surveys) at four time points: at the time of ED admission, and at 7-days, 30-days, and 90-days after ED admission. Outpatient participants in the Telehealth study will be asked to complete study sessions at three time points: baseline, 30- and 90-days after the initial session. The initial session of the ED study will be conducted in-person in a private space provided by the organization/hospital (e.g., the patient’s room or another private environment); the initial session of the Telehealth study will be conducted remotely. Each follow up assessment will be conducted remotely consisting of a brief phone

interview and a set of surveys administered online.

The ED study will also include provider participants who will be asked to complete a demographics survey and a brief interview about each of their index study patients after their intervention with the patient is complete. The brief interview will be administered in-person and assess the provider's feeling of preparedness for the assessment, the patient's degree of distress at the time of encounter, helpfulness of Jaspr's clinical support tool in discharge disposition determination, and risk assessment (if applicable).

ED study primary outcome variables include: suicidality (death by suicide, suicide attempts, suicidal ideation), ED/hospital admissions, discharge disposition, use of restraints while in ED (chemical, physical), intensity ratings of acute distress, self-efficacy in coping with distress, use of imminent distress intervention and coping skills, and helpfulness of their ED encounter. Jaspr condition-specific outcomes will be examined and reported descriptively. These include tools accessed during and after the ED visit, perceived usefulness and satisfaction of Jaspr brief intervention components, and usage of provider/patient apps and their features.

Telehealth study primary outcome variables include: suicidality (death by suicide, suicide attempts, suicidal ideation); Crisis-related healthcare utilization (ED visits, psychiatric hospitalization, calls to crisis line; crisis calls to therapist; Outpatient Satisfaction; Use of evidence-based interventions to reduce suicide risk (safety planning, lethal means management, behavioral skills). Secondary outcomes include: Reasons for living; Psychological distress (depression, anxiety, stress); Cognitions associated with suicide risk (hope, optimism, pessimism).

The primary hypotheses include:

1. Jaspr patients will report significantly greater decrease in suicidality and ED/hospital admissions than CAU patients from the initial session to follow-up assessments.
2. Jaspr patients will report significantly greater increases in self-efficacy in coping with acute distress, use of acute crisis tolerance skills, and perceived helpfulness of the care they receive compared to CAU patients.
3. Jaspr patients will report high levels of satisfaction with Jaspr.

Secondary hypotheses for the ED study include that medical providers will rate the Jaspr clinical support tools as helpful in preparing for and assessing suicide risk and patient's degree of distress at the time of their encounter and aiding in discharge disposition plan. We will also examine if providers rate themselves as more confident in their suicide risk assessment with patients assigned to the Jaspr condition compared to those assigned to the CAU condition.

The procedures defined within this document pertain *only* to the procedures performed during the summative evaluation.

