## **B. Analysis of Study Results**

During the summative evaluation, data gathered is qualitative and quantitative in nature. Online survey measures will be administered at four time points (baseline, post treatment, 7-day follow up, 30-day follow up, and 90-day follow up) to all ED study patient participants and three time points (baseline, 30-day, and 90-day follow up) to all Telehealth study participants. For the ED study, provider participants will complete study procedures via interview with the researcher (on paper or online if they prefer) at post treatment for all patients they treat as part of this study. Measures for patient

participants will include demographics, questions about suicidality, depressive symptoms, use of acute crisis tolerance skills, coping with acute distress, and satisfaction with ED experience. Measures for provider participants will include demographics, questions about preparedness for clinical interview, patient distress, provider confidence in suicide risk assessment, and helpfulness of Jaspr. Semi-structured interviews will be conducted with patient participants at each time point after baseline to obtain feedback about the participant's experience in the ED, experience with suicide symptoms, and/or Jaspr tools and features. For the Telehealth study, measures for patient participants include demographics, questions about suicidality, depressive and anxiety symptoms, stress, coping with acute distress, satisfaction with outpatient care and JAH. Semi-structured interviews at each follow-up assessment will be conducted to obtain feedback about the participant's experience with suicide and use of their resources since the prior study session.

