***Analysis Strategy.*** We will use SPSS Version 23. For patient data, we will use Hierarchical Linear Modeling (HLM). HLM provides greater flexibility in that it can analyze a variety of commonly encountered outcome distributions (e.g., continuous, binary count), test the fit of different covariance matrix assumptions; and include participants who are missing data at some time points. We will account for nesting of patients under providers by including providers as a random effect; we will account for nesting within sites by including dummy coded fixed effects predictors representing site in all analyses. For each outcome, we will specify the correct distribution and compare fit indices to identify the covariance matrix best fitting the data. Many hypotheses relate to change over time, and so the multiple time-points will be treated as nested within the individual. Also, we will treat the intervention conditions (Jaspr and JAH) and time as categorical, dummy-coded predictors; the control conditions and baseline scores will serve as the reference category. The parameter of interest will be the Time X Condition interaction, and the Type III statistic will serve as an omnibus test of whether the two conditions differed in change over time. Regression coefficients will indicate at which follow up time points the conditions showed differential change from baseline. For patient satisfaction as well as the secondary hypotheses concerning medical providers ratings of helpfulness, we will compute descriptive statistics and consider ratings to be favorable using the *a priori* established criteria that 80% or more respondents rate program components as favorable or highly favorable. For the remaining secondary hypotheses, which are based on provider data about patients from both conditions at one time point, we will compute between-condition means. Since it is possible that not all providers will be able to provide data given time constraints inherent in their job, we may not have the statistical power to conduct probability tests. Hence, we will examine the data descriptively to provide preliminary information about efficacy and compute effect sizes to inform future research.

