***Statistical Power Considerations.*** For Hypotheses 1 and 2, we conducted power analyses focused on the ability to detect statistical significance on the key parameter of interest, the Time X Condition interaction. Power analyses assumed equal size groups,  $p \leq .05$ , power of .80, and two-tailed tests. Using GPower's utility for the General Linear Model, we found that a total sample size of 24 patients would allow detection a medium effect ( $f > = 25$ ). However, this assumes no design effects (DE) that occur due to the nesting of patients under physicians. In the likely event that design effects exist, a sample of 72 participants will allow sufficient power to detect a medium effect with DEs as great as 3.0). Adjusting this number for possible 20% attrition, we would need to enroll at least 90 patients, but will strive to include 120 patients total in this research to ensure we have sufficient statistical power for all outcome variables.

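### Hypothesis 2 tests helpfulness of the ED encounter as change from a baseline taken before the intervention; a between-arm comparison of the later ratings would fit the question better and have more power

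*Combined protocol and SAP*

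**What the plan says.** The Introduction (section 3) lists among the ED study's primary outcomes "use of imminent distress intervention and coping skills, and helpfulness of their ED encounter". Hypothesis 2 predicts greater increases under Jaspr in several outcomes, including "use of acute crisis tolerance skills, and perceived helpfulness of the care they receive compared to CAU patients".

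Section 5.B, Analysis Strategy, states: "The parameter of interest will be the Time X Condition interaction, and the Type III statistic will serve as an omnibus test". It treats time as categorical, and "the control conditions and baseline scores will serve as the reference category". Statistical Power Considerations applies this parameter to Hypothesis 2: "For Hypotheses 1 and 2, we conducted power analyses focused on the ability to detect statistical significance on the key parameter of interest".

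On timing, the Introduction places the ED study sessions "at the time of ED admission, and at 7-days, 30-days, and 90-days after ED admission". Section 5.A (ED Study) has the patient complete baseline measures, then learn the assigned condition, then use Jaspr or receive usual care for up to two hours, then complete the post-treatment surveys.

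Section 5.B names the patient measures, among them "use of acute crisis tolerance skills, coping with acute distress, and satisfaction with ED experience". It gives no schedule of measures by visit. It says that the online surveys are given at baseline, post treatment and days 7, 30 and 90. The semi-structured interviews, which ask about the ED experience, take place only after baseline.

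**The concern.** Change from baseline makes sense when the same quantity can be measured before and after the intervention. Self-efficacy qualifies. Helpfulness of the ED encounter does not, because at baseline most of what is to be judged, including the study intervention, has not happened. Two cases follow.

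- **Rated at baseline.** The reference is a rating of care so far, which may be only weakly related to a later rating of the encounter. Subtracting it adds noise.
- **First rated at post treatment.** There is no baseline score. If the first available rating becomes the reference, an arm difference already present then and constant afterwards drops out of the interaction.

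Hypothesis 2 is a primary hypothesis. Jaspr patients could rate their care higher at every later visit and the prespecified test could still miss it. Moving to a direct arm comparison after seeing the data would look post hoc.

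**Working it through.** **The plan's own figure.** Inputs from Statistical Power Considerations are a medium effect (read as f = .25), two-sided alpha .05, power .80 and equal groups. The repeated-measures interaction formula is λ = f²·N·m/(1−ρ), with m−1 and (N−2)(m−1) degrees of freedom. Taking m = 4 measurements and ρ = .5 (ρ is not in the plan), λ = .0625 × 24 × 4/.5 = 12 with 3 and 66 df, and power is .816. So 24 reproduces; with m = 5 it would be 22. Then 24 × 3 = 72 and 72/.8 = 90, as stated. The calculation presupposes a like-for-like baseline for every Hypothesis 2 outcome.

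**Assumptions for the comparison** (not in the plan). The benefit is d = 0.5 SD at post treatment and days 7, 30 and 90. This is the two-group counterpart of f = .25, since f = d/2. The correlation among these four ratings is ρ = .5, and each correlates b with the baseline rating. There is no clustering. From the plan's target and attrition, n = 120 × .8/2 = 48 per arm.

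**Formulas.** The mean of the four later ratings has variance (1 + 3ρ)/4 = .625. Its change from baseline has variance v = .625 + 1 − 2b. In both cases λ = n·d²/(2v) = 48 × .25/(2v) = 6/v. The one-df test is a t test with 94 df. The planned omnibus test has the same λ but 4 and (96−2) × 4 = 376 df.

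**Case 1, rated at baseline, 48 per arm**

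| b | v | λ | Power, 1-df change | Power, planned omnibus |
|---|---|---|---|---|
| 0 | 1.625 | 3.69 | .48 | .29 |
| .2 | 1.225 | 4.90 | .59 | .38 |
| .4 | .825 | 7.27 | .76 | .55 |
| .5 | .625 | 9.60 | .87 | .69 |

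**Averaged arm difference, no baseline used.** Here v = .625 and λ = 9.60, giving power .87 (.94 at ρ = .3, where v = .475; .79 at ρ = .7, where v = .775). With baseline as a covariate, v = .625 − b², which is .585 at b = .2 (power .89) and .465 at b = .4 (power .94). A contrast at post treatment alone has v = 1 and λ = 6.0, giving .68.

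**Separating the two losses.** At b = .5 the one-df change test matches the averaged difference (.87), so the fall to .69 is entirely due to degrees of freedom. The fall from .87 to .48–.76 at b = 0 to .4 is the cost of the weak baseline.

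**At 60 per arm (no attrition).** The omnibus test has .36 at b = 0, .56 at b = .3 and .80 at b = .5. The averaged difference has .93.

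**Case 2, first rated at post treatment.** Each interaction contrast is .5 − .5 = 0, so λ = 0 and rejection is 5% at any sample size. If the benefit instead faded as .5, .33, .17, 0, the interaction would reject with power .67 at 60 per arm, but because the advantage was being lost.

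**The case against.** A reader might infer that helpfulness cannot be rated at baseline at all. The documents do not support that. Section 4.A requires patients to have been judged stable by ED personnel or another treating provider, and section 7.A has site staff identify suitable patients first. An enrolled patient has normally had some care to rate. What cannot be rated then is the encounter as a whole.

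A reader might also infer that the planned test has no power for a lasting benefit. That holds only in case 2. Section 5.B reads most naturally as giving the surveys at baseline as well, since only the interviews are confined to later visits, and nowhere does the plan make post treatment the reference. In case 1, randomisation keeps the test valid and a lasting benefit is visible. Even in case 2 the fitted model would show the arm difference at its reference visit, although that is not the parameter named for Hypothesis 2.

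Three further points deserve weight.

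- Comparing the omnibus test directly with the averaged difference overstates the baseline problem, because part of that gap is degrees of freedom. That cost applies to self-efficacy too.
- Using 48 per arm removes 20% at every visit, although the planned model keeps partial responders. At 60 per arm and b = .5 the omnibus test reaches .80, the plan's own target.
- Hypothesis 2 speaks of the care patients receive. That could include the take-home app and post-discharge contacts, so the rated object could change during follow-up. The primary outcome list names the ED encounter. The two labels should be reconciled.

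The 80% favourable-rating criterion in the Analysis Strategy does not answer the concern. It is descriptive, concerns ratings of program components, and provides no between-arm test.

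**Conclusion.** The concern holds in a limited form. The plan ties a primary helpfulness outcome to change from a baseline that is not like-for-like, and the stated test is inferior whichever visit comes first. In the more natural case it is valid but weaker: .48 to .76 for a one-df change from baseline, and .29 to .55 for the planned omnibus test, against .87 for the averaged arm difference. In the other case, which the text does not settle, a constant benefit is rejected only 5% of the time.

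The powers rest on assumed values for the benefit, its constancy, the correlations and the absence of clustering; clustering could lower all of them except the 5%. If the baseline rating correlated .5 or more with later ones, the loss due to the baseline itself would disappear and only the degrees-of-freedom cost would remain.

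**What to change.** For this outcome only:

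- Restate Hypothesis 2 as higher perceived helpfulness of the ED encounter than under CAU.
- Fix the referent as the index ED encounter at every rating, and state the visits at which it is asked. The post-treatment rating is also taken in the ED, so the item should say what period it covers.
- Make the primary test the condition effect averaged over the post-randomisation ratings, with the planned site and provider terms. The effect at post treatment alone is an alternative, at lower power under these assumptions (.68 at 48 per arm).
- If care so far is rated at baseline, enter it as a covariate and not as the reference for change.

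Keep the Time X Condition test for outcomes with a like-for-like baseline, such as self-efficacy.

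The cost is a change of hypothesis wording and one model specification, made before outcome data are examined. The claim becomes higher than CAU instead of a greater increase. No additional data are required.
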